3.7 Eligibility Checklist

Before the patient can be enrolled, the responsible institutional investigator must sign and date the completed eligibility checklist. A signed copy of the checklist will be uploaded into RAVE immediately following enrollment.

3.8 Institutional Pathology Report

Immediately following enrollment, the institutional pathology report for the diagnosis under which the patient is being enrolled must be uploaded into RAVE. The report must include the associated study number and COG patient registration and accession numbers. Personal identifiers, including the patient's name and initials must be removed from the institutional pathology report prior to submission.

3.9 Study Enrollment

Patients may be enrolled on the study once all eligibility requirements for the study have been met. Patients who give informed consent for the protocol in order to undergo screening for eligibility are not considered enrolled and should not be enrolled until the screening is completed and they are determined to meet all eligibility criteria. Study enrollment is accomplished by going to the CTSU OPEN (Oncology Patient Enrollment Network) <https://open.ctsu.org/open/>. For questions, please contact the COG Study Research Coordinator, or the CTSU OPEN helpdesk at <https://www.ctsu.org/CTSUContact.aspx>. Patients must be enrolled before treatment begins. The date protocol therapy is started must be no later than five (5) calendar days after the date of study enrollment. **Patients must not receive any protocol therapy prior to enrollment.**

3.10 Dose Assignment

The dose level will be assigned via OPEN at the time of study enrollment.

4.0 PATIENT ELIGIBILITY

All clinical and laboratory studies to determine eligibility must be performed within 7 days prior to enrollment unless otherwise indicated. Laboratory values used to assess eligibility must be no older than seven (7) days at the start of therapy. Laboratory tests need **not** be repeated if therapy starts **within** seven (7) days of obtaining labs to assess eligibility. If a post-enrollment lab value is outside the limits of eligibility, or laboratory values are older than 7 days, then the following laboratory evaluations must be re-checked within 48 hours prior to initiating therapy: CBC with differential, bilirubin, ALT (SGPT) and serum creatinine. If the recheck is outside the limits of eligibility, the patient may not receive protocol therapy and will be considered off protocol therapy. Imaging studies must be obtained within 14 days prior to start of protocol therapy (repeat the tumor imaging if necessary).

Clarification in timing when counting days: As an example, please note that if the patient's last day of prior therapy is September 1st, and the protocol requires waiting at least 7 days for that type of prior therapy, then that patient cannot be enrolled until September 8th.

Important note: The eligibility criteria listed below are interpreted literally and cannot be waived (per COG policy posted 5/11/01). All clinical and laboratory data required for determining eligibility of a patient enrolled on this trial must be available in the patient's medical or research record which will serve as the source document for verification at the time of audit.

4.1 Inclusion Criteria

- 4.1.1 Age: Patients must be \geq than 12 months and \leq 21 years of age at the time of study enrollment.
- 4.1.2 Patients must have a BSA of $\geq 1.17 \text{ m}^2$ at time of study enrollment.
- 4.1.3 Patients must be able to swallow intact tablets.
- 4.1.4 Diagnosis: Patients with recurrent or refractory solid tumors, including CNS tumors or lymphoma, are eligible. Patients must have had histologic verification of malignancy at original diagnosis or relapse except in patients with intrinsic brain stem tumors, optic pathway gliomas, or patients with pineal tumors and elevations of CSF or serum tumor markers including alpha-fetoprotein or beta-HCG.
- 4.1.5 Disease Status:
Patients must have either measurable or evaluable disease (see Sections [12.2](#) and [12.3](#) for definitions).
- 4.1.6 Therapeutic Options: Patient's current disease state must be one for which there is no known curative therapy or therapy proven to prolong survival with an acceptable quality of life.
- 4.1.7 Performance Level: Karnofsky $\geq 50\%$ for patients > 16 years of age and Lansky ≥ 50 for patients ≤ 16 years of age (See [Appendix I](#)). Note: Neurologic deficits in patients with CNS tumors must have been relatively stable for at least 7 days prior to study enrollment. Patients who are unable to walk because of paralysis, but who are up in a wheelchair, will be considered ambulatory for the purpose of assessing the performance score.
- 4.1.8 Prior Therapy
Patients must have fully recovered from the acute toxic effects of all prior anti-cancer therapy and must meet the following minimum duration from prior anti-cancer directed therapy prior to enrollment. If after the required timeframe, the defined eligibility criteria are met, e.g. blood count criteria, the patient is considered to have recovered adequately.
- a. Cytotoxic chemotherapy or other anti-cancer agents known to be myelosuppressive. See DVL homepage for commercial and Phase I investigational agent classifications. For agents not listed, the duration

of this interval must be discussed with the study chair and the study-assigned Research Coordinator prior to enrollment.

i. *Solid Tumor Patients*: ≥ 21 days after the last dose of cytotoxic or myelosuppressive chemotherapy (42 days if prior nitrosourea).

ii. *Lymphoma Patients*:

- A waiting period prior to enrollment is not required for patients receiving standard cytotoxic maintenance chemotherapy (i.e. corticosteroid, vincristine, 6MP, and/or methotrexate).
- ≥ 14 days must have elapsed after the completion of other cytotoxic therapy, with the exception of hydroxyurea, for patients not receiving standard maintenance therapy. Additionally, patients must have fully recovered from all acute toxic effects of prior therapy.

Note: Cyto-reduction with hydroxyurea must be discontinued ≥ 24 hours prior to the start of protocol therapy.

b. Anti-cancer agents not known to be myelosuppressive (e.g. not associated with reduced platelet or ANC counts): ≥ 7 days must have elapsed from the last dose of agent. See DVL homepage for commercial and Phase 1 investigational agent classifications. For agents not listed, the duration of this interval must be discussed with the study chair and the study-assigned Research Coordinator prior to enrollment.

c. Antibodies: ≥ 21 days must have elapsed from infusion of last dose of antibody, and toxicity related to prior antibody therapy must be recovered to Grade ≤ 1 .

d. Hematopoietic Growth Factors: ≥ 14 days must have elapsed from the last dose of a long-acting growth factor (e.g. Pegfilgrastim) or 7 days for short-acting growth factor. For agents that have known adverse events occurring beyond 7 days after administration, this period must be extended beyond the time during which adverse events are known to occur. The duration of this interval must be discussed with the study chair and the study-assigned Research Coordinator.

e. Interleukins, Interferons and Cytokines (other than Hematopoietic Growth Factors): ≥ 21 days must have elapsed from the last dose of interleukins, interferon or cytokines (other than Hematopoietic Growth Factors).

f. Stem cell Infusions (with or without TBI):

- Allogeneic (non-autologous) bone marrow or stem cell transplant, or any stem cell infusion including DLI or boost infusion: ≥ 84

days must have elapsed from infusion and no evidence of GVHD.

- Autologous stem cell infusion including boost infusion: ≥ 42 days must have elapsed from infusion.
- g. Cellular Therapy: ≥ 42 days must have elapsed from last dose of any type of cellular therapy (e.g. modified T cells, NK cells, dendritic cells, etc.)
- h. XRT/External Beam Irradiation including Protons: ≥ 14 days must have elapsed after local XRT; ≥ 150 days after TBI, craniospinal XRT or if radiation to $\geq 50\%$ of the pelvis; ≥ 42 days if other substantial BM radiation.
- i. Radiopharmaceutical Therapy (e.g., radiolabeled antibody, 131I-MIBG): ≥ 42 days must have elapsed from the last dose of systemically administered radiopharmaceutical therapy.
- j. HDAC Inhibitors: Patients must not have received prior therapy with entinostat. Patients who have received therapy with other HDAC inhibitors are eligible.

4.1.9 Organ Function Requirements

4.1.9.1 Adequate Bone Marrow Function Defined as:

- a. For patients with solid tumors, including lymphoma, without known bone marrow involvement:
 - Peripheral absolute neutrophil count (ANC) $\geq 1000/\text{mm}^3$
 - Platelet count $\geq 100,000/\text{mm}^3$ (transfusion independent, defined as not receiving platelet transfusions for at least 7 days prior to enrollment)
 - Hemoglobin ≥ 8.0 g/dl, with or without transfusion
- b. Patients with known bone marrow metastatic disease will not be eligible.

4.1.9.2 Adequate Renal Function Defined as:

- Creatinine clearance or radioisotope GFR $\geq 70\text{ml}/\text{min}/1.73 \text{ m}^2$ or
- A serum creatinine based on age/gender as follows:

Age	Maximum Serum Creatinine (mg/dL)	
	Male	Female
1 to < 2 years	0.6	0.6

2 to < 6 years	0.8	0.8
6 to < 10 years	1	1
10 to < 13 years	1.2	1.2
13 to < 16 years	1.5	1.4
≥ 16 years	1.7	1.4

The threshold creatinine values in this Table were derived from the Schwartz formula for estimating GFR³³ utilizing child length and stature data published by the CDC.

4.1.9.3 Adequate Liver Function Defined as:

- Bilirubin (sum of conjugated + unconjugated) ≤ 1.5 x upper limit of normal (ULN) for age
- SGPT (ALT) ≤ 3 × ULN = 135 U/l. For the purpose of this study, the ULN for SGPT is 45 U/l.
- Serum albumin ≥ 2 g/dl.

4.1.10 Informed Consent: All patients and/or their parents or legally authorized representatives must sign a written informed consent. Assent, when appropriate, will be obtained according to institutional guidelines.

4.2 **Exclusion Criteria**

4.2.1 Pregnancy or Breast-Feeding:

Pregnant or breast-feeding women will not be entered on this study due to risks of fetal and teratogenic adverse events as seen in animal studies. Pregnancy tests must be obtained in girls who are post-menarchal. Males or females of reproductive potential may not participate unless they have agreed to use an effective contraceptive method both during and for 3 months after participation in this study. Abstinence is an acceptable method of contraception. Those who become pregnant while on treatment with entinostat must discontinue immediately and consult their treating physician.

4.2.2 Concomitant Medications

4.2.2.1 Corticosteroids:

Patients receiving corticosteroids who have not been on a stable or decreasing dose of corticosteroid for at least 7 days prior to enrollment are not eligible. If used to modify **immune adverse events** related to prior therapy, ≥ 14 days must have elapsed since last dose of corticosteroid.

4.2.2.2 Investigational Drugs:

Patients who are currently receiving another investigational drug are not

eligible.

4.2.2.3 Anti-cancer Agents:

Patients who are currently receiving other anti-cancer agents are not eligible.

4.2.2.4 Patients requiring concurrent administration of valproic acid are not eligible for this trial.

4.2.2.5 Anti-GVHD agents post-transplant:

Patients who are receiving cyclosporine, tacrolimus or other agents to prevent graft-versus-host disease post bone marrow transplant are not eligible for this trial.

4.2.3 Study Specific:

- Patients with a BSA < 1.17 m² at time of study enrollment are not eligible.
- Patients who are not able to swallow intact tablets are not eligible.

4.2.4 Cardiac:

Patients with a known history of QTc prolongation (> 480 msec), or known history of ventricular tachycardia, ventricular fibrillation or Torsades de pointes are not eligible.

4.2.5 Infection:

Patients who have an uncontrolled infection are not eligible.

4.2.6 Transplantation:

Patients who have received a prior solid organ transplantation are not eligible.

4.2.7 Patients who in the opinion of the investigator may not be able to comply with the safety monitoring requirements of the study are not eligible.

4.2.8 Patients with a history of allergy to medications that have a benzamide structure (e.g., metoclopramide, procarbazine, domperidone, cisapride etc.) are not eligible.

5.0 TREATMENT PROGRAM

5.1 Overview of Treatment Plan

		Entinostat oral	Action
Week 1	Day 1	X	
Week 2	Day 8	X	
Week 3	Day 15	X	
Week 4	Day 22	X	
End of Cycle	Day 28		Evaluation

Entinostat will be administered orally on Days 1, 8, 15, and 22 of a 28-day cycle. Patients may continue to receive entinostat for up to 5 years.

Drug doses should be adjusted based on the BSA calculated from height and weight measured within 7 days prior to the beginning of each cycle. If a patient vomits within 30 minutes after the dose of entinostat is administered, that dose may be repeated. If vomiting occurs greater than 30 minutes after the administered dose, the dose will not be repeated. If a patient misses an entinostat dose and less than 12 hours have passed since the scheduled dosing time, that dose should be taken immediately. If a patient misses an entinostat dose and more than 12 hours have passed since the scheduled dosing time, this dose will be skipped. If a patient accidentally takes an extra dose during a day, the next scheduled dose of entinostat will be skipped.

The patient/family will be asked to complete a Patient Medication Diary (see [Appendix V](#)).

5.2 Criteria for Starting Subsequent Cycles

A cycle may be repeated every 28 days if the patient has at least stable disease and has again met laboratory parameters as defined in the eligibility section, [Section 4.0. Section 4.0](#)

5.3 Dose Escalation Schema

5.3.1 Inter-Patient Escalation

The starting dose will be 3 mg/m² (dose level 1) with dose levels for subsequent groups of patients as follows.

Dose Level	Entinostat (mg/m ²)	Day(s) of Administration
- 1	2.3	1, 8, 15, 22
1*	3	1, 8, 15, 22
2	4	1, 8, 15, 22

*Starting dose level of ~ adult RP2D

There will be no escalations beyond dose level 2 (4 mg/m²), as previous pediatric Phase 1 studies have rarely defined a MTD greater than 160% of the adult MTD.

If the MTD has been exceeded at the first dose level, then the subsequent cohort of patients will be treated at a dose of 2.3 mg/m² (dose level -1). If dose level -1 is not well tolerated, further de-escalation will not occur. The study will be closed to accrual.

Entinostat doses will be rounded to the nearest 1 mg (see dosing tables in [Appendix IV](#)).

5.3.2 Intra-Patient Escalation

Intra-patient dose escalation is not allowed.

5.4 **Grading of Adverse Events**

Adverse events (toxicities) will be graded according to the NCI Common Terminology Criteria for Adverse Events (CTCAE) version 5.0. All appropriate treatment areas should have access to a copy of the CTCAE version 5.0. A copy of the CTCAE version 5.0 can be downloaded from the CTEP website (http://ctep.cancer.gov/protocolDevelopment/electronic_applications/ctc.htm). Any suspected or confirmed dose-limiting toxicity should be reported immediately (within 24 hours) to the Study Chair.

5.5 **Definition of Dose-Limiting Toxicity (DLT)**

DLT will be defined as any of the following events that are possibly, probably or definitely attributable to protocol therapy. The DLT observation period for the purposes of dose-escalation will be the first cycle of therapy.

Dose limiting hematological and non-hematological toxicities are defined differently.

5.5.1 Non-Hematological Dose-Limiting Toxicity

5.5.1.1 Any Grade 3 or greater non-hematological toxicity attributable to the investigational drug with the specific exclusion of:

- Grade 3 nausea and vomiting of less < 3 days duration
- Grade 3 liver enzyme elevation, including ALT/AST/GGT that returns to levels that meet initial eligibility criteria or baseline within 7 days. See [Appendix III](#) for values that represent thresholds between CTCAE grades. Note: For the purposes of this study the ULN for ALT is defined as 45 U/L.
- Grade 3 or 4 fever < 5 days duration.
- Grade 3 infection < 5 days duration.
- Grade 3 hypophosphatemia, hypokalemia, hypocalcemia or hypomagnesemia responsive to supplementation.
- Any Grade 2 non-hematological toxicity that persists for ≥ 7 days and is considered sufficiently medically significant or sufficiently intolerable by patients that it requires treatment interruption.
- Note: Allergic reactions that necessitate discontinuation of study drug will not be considered a dose-limiting toxicity.

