2.4.1 Prior Experience in Children

There have been no prior pediatric studies with entinostat.

2.5 **Overview of Proposed Pediatric Study**

This will be a phase 1 dose-escalation trial of entinostat in pediatric patients with recurrent or refractory solid tumors including CNS tumors and lymphoma. The primary study objectives are to identify the maximum tolerated dose (MTD) or recommended phase 2 dose (RP2D), characterize the toxicity profile, evaluate the change in histone acetylation, and describe the pharmacokinetics of entinostat in pediatric patients with solid tumors.

Patients age 1 to 21 years with recurrent or refractory solid tumors, including CNS tumors and lymphoma will be eligible. Entinostat will be administered orally at a starting dose of 3 mg/m² once weekly, which is equivalent to the RP2D of 5 mg in adults when entinostat is administered on a weekly schedule. Entinostat will be administered continuously once weekly in 28-day cycles. Cohorts will be enrolled and doses escalated using the rolling six design.³² Doses will be escalated by approximately 30% in each subsequent cohort.

The MTD will be determined from toxicities observed during the first cycle of treatment. The MTD will be the dose level below which ≥ 2 out of a cohort of up to 6 patients experience DLTs. Disease evaluations will be performed at the end of Cycle 1, then every other cycle for 2 cycles, then every 3 cycles. Pharmacokinetic and pharmacodynamic sampling will be performed during the 1st cycle of treatment.

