8.0 EVALUATIONS/MATERIAL AND DATA TO BE ACCESSIONED

8.1 Required Clinical, Laboratory and Disease Evaluation

All clinical and laboratory studies to determine eligibility must be performed within 7 days prior to enrollment unless otherwise indicated. Laboratory values used to assess eligibility (see [Section 4.0](#)) must be no older than seven (7) days at the start of therapy. Laboratory tests need **not** be repeated if therapy starts **within** seven (7) days of obtaining labs to assess eligibility. If a post-enrollment lab value is outside the limits of eligibility, or laboratory values are older than 7 days, then the following laboratory evaluations must be re-checked within 48 hours prior to initiating therapy: CBC with differential, bilirubin, ALT (SGPT) and serum creatinine. If the recheck is outside the limits of eligibility, the patient may not receive protocol therapy and will be considered off protocol therapy. Imaging studies must be obtained within 14 days prior to start of protocol therapy (repeat the tumor imaging if necessary).

STUDIES TO BE OBTAINED	Pre-Study	During Cycle 1	Prior to Subsequent Cycles[^]
History	X	Weekly	X
Physical Exam with vital signs	X	Weekly	X
Height, weight, BSA	X		X
Performance Status	X		
CBC, differential, platelets	X	Twice Weekly	Weekly ³
Pharmacokinetics ¹	X	X	X
Urinalysis	X		
Electrolytes including Ca ²⁺ , PO ₄ ³⁻ , Mg ²⁺ ; glucose	X	Weekly	X
Creatinine, ALT, bilirubin	X	Weekly	X
Albumin	X		X
Tumor Disease Evaluation	X	End of Cycle 1	Every other cycle x 2 then q 3 cycles ⁴
Pharmacodynamics Studies (H3 and H4 Histone Acetylation in PBMCs) ⁶	X	X ⁷	
Pregnancy Test ²	X		
Patient Diary ⁵		Weekly	X

[^] Studies may be obtained within 72 hours prior to the start of the subsequent cycle.

¹ See [Section 8.3](#) for timing of PK studies.

² Women of childbearing potential require a negative pregnancy test prior to starting treatment; sexually active patients must use an acceptable method of birth control. Abstinence is an acceptable method of birth control. Patients of reproductive potential must use secure methods of contraception during treatment and for 3 additional months after the end of treatment. Those who become pregnant while on treatment with entinostat must discontinue immediately and consult their treating physician.

³ If patients develop Grade 4 neutropenia or Grade 4 thrombocytopenia then CBCs should be checked every 3 to 4 days until recovery to Grade 3.

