10.0 CRITERIA FOR REMOVAL FROM PROTOCOL THERAPY AND OFF STUDY CRITERIA

10.1 Criteria for Removal from Protocol Therapy

- a) Clinical (including physical examination or serum tumor markers) or radiographic evidence of progressive disease (See [Section 12.0](#)).
- b) Adverse Events requiring removal from protocol therapy (See [Section 5.2](#) [Section 6.0](#)).
- c) Refusal of protocol therapy by patient/parent/guardian
- d) Non-compliance that in the opinion of the investigator does not allow for ongoing participation.
- e) Physician determines it is not in the patient's best interest.
- f) Repeated eligibility laboratory studies (CBC with differential, bilirubin, ALT (SGPT) or serum creatinine) are outside the parameters required for eligibility prior to the start of entinostat (See [Section 8.1](#)).
- g) Study is terminated by Sponsor.
- h) Pregnancy.

Patients who are removed from protocol therapy during cycle 1 should continue to have the required observations in [Section 8.1](#) until the originally planned end of the cycle or until all adverse events have resolved per [Section 13.4.4](#), whichever happens LATER. The only exception is with documentation of the patient's withdrawal of consent. Patients who are removed from protocol therapy in subsequent cycles should have the necessary observations to ensure adequate clinical care.

Patients who are off protocol therapy are to be followed until they meet the criteria for Off Study (see below). Ongoing adverse events, or adverse events that emerge after the patient is removed from protocol therapy, but within 30 days of the last dose of investigational agent, must be followed and reported via RAVE and CTEP-AERS (if applicable). Follow-up data will be required unless consent is withdrawn.

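### A Grade 3 albumin fall in Cycle 1 counts as a DLT, but a patient who takes all four doses and leaves before the pre-Cycle 2 labs can be scored DLT-free with no albumin required after baseline

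*Combined protocol and SAP*

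**What the plan says.** **DLT definition (protocol Section 5.5.1.1).** A DLT is "Any Grade 3 or greater non-hematological toxicity attributable to the investigational drug with the specific exclusion of" listed items. The laboratory items excluded are Grade 3 liver enzyme rises that recover within 7 days and "Grade 3 hypophosphatemia, hypokalemia, hypocalcemia or hypomagnesemia responsive to supplementation". Albumin is in neither. Section 5.5 sets the observation period as the first cycle.

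**Monitoring (Section 8.1 table).** The row "Creatinine, ALT, bilirubin" is marked pre-study, weekly during Cycle 1, and before later cycles. The electrolyte row follows the same pattern. The albumin row is marked pre-study and before later cycles, and its Cycle 1 cell is blank. A footnote ties the later draw to the next cycle: "Studies may be obtained within 72 hours prior to the start of the subsequent cycle".

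**Who reaches that draw.** Section 2.5 states: "Disease evaluations will be performed at the end of Cycle 1". Section 5.2 allows a further cycle "if the patient has at least stable disease and has again met laboratory parameters as defined in the eligibility section". Those parameters include "Serum albumin ≥ 2 g/dl" (Section 4.1.9.3).

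**After removal in Cycle 1 (Section 10.1).** The Section 8.1 observations continue "until the originally planned end of the cycle or until all adverse events have resolved per" Section 13.4.4, whichever is later.

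**Evaluability (Section 11.2.1).** In the dose-escalation portion, a patient without DLT must have had at least 85% of the prescribed dose and suitable toxicity monitoring. The tests are not listed.

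**The concern.** The DLT count drives the dose decision, and that decision can turn on one patient. Hypoalbuminemia is a foreseeable event: Section 2.3.1 names three DLTs in the adult trial that dosed weekly for four weeks of a six-week cycle, namely low phosphate, low sodium and low albumin. The Section 8.1 table checks electrolytes every week of Cycle 1 but has no Cycle 1 entry for albumin.

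A fall in albumin that shows only in the laboratory is not seen unless someone orders the test. If the plan counts the event but does not require the measurement in some evaluable patients, the error runs one way: events can be lost and none can be added. A dose level then looks more tolerable than it is. Section 11.2.2 adds DLTs from the PK expansion to the count at the MTD, but nothing in the documents gives those patients a different laboratory schedule, so pooling does not correct the loss.

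**Working it through.** The plan gives no figure for this point, so there is none to reproduce. The check follows one patient through the sections.

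**1. Required albumin values after baseline**

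| Patient (all four doses taken) | Required albumin after baseline |
|---|---|
| Starts Cycle 2 | 1, within 72 hours before Cycle 2 (Day 1 of Cycle 2 is Day 29, so from Day 26) |
| Kept out of Cycle 2 because the repeat labs fail | Labs drawn, so a value is expected |
| Leaves after the labs were drawn in the 72-hour window | Labs drawn, so a value is expected |
| Leaves before those labs are drawn | 0 |

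Only the last row is the gap. Weekly analytes have about four values over the same cycle.

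**2. Is that patient counted?** Doses fall on Days 1, 8, 15 and 22. Four of four is 100%, above 85%, so the dose condition is met. The monitoring condition in Section 11.2.1 can only be read against Section 8.1, whose Cycle 1 column has no albumin. The patient can be entered as without DLT. Section 10.1 extends the Section 8.1 observations, but these add no albumin.

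**3. Patients who stop earlier.** Three of four doses is 3/4 = 75%, below 85%. In the dose-escalation portion such a patient, if DLT-free, is replaced. Section 11.2.1 states this condition only for that portion, so PK-expansion patients who stop early may also be affected.

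**4. Effect of one lost event**

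- Section 11.3: 2 of 6 means the MTD is exceeded; 1 of 6 passes.
- Section 11.2.2, if six escalation and six PK patients are pooled (6 + 6 = 12): 4/12 = 33.3% is exceeded; 3/12 = 25% is not.
- If the level passed on three patients and six PK patients follow (3 + 6 = 9): 3/9 = 33.3% is exceeded; 2/9 = 22.2% is not.

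**5. Illustration on assumed inputs.** None of these rates is in the documents.

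- a = share of patients whose only DLT is a Grade 3 albumin fall: 3% (range 1% to 5%)
- s = share taking four doses and not starting Cycle 2: 35% (range 20% to 50%)
- u = share of those who leave before the labs are drawn: 0.5 to 1
- true DLT rate: 25%

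Hidden rate h = a × s × u, and observed rate q = 0.25 − h. With complete data, the first decision passes on 0 of 3, or on 1 of 3 followed by 0 of the next 3:

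P(pass) = (1 − q)³ + 3q(1 − q)⁵

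| a, s | u | h | P(pass) |
|---|---|---|---|
| nothing hidden | – | 0 | 0.600 |
| 1%, 20% | 0.5 | 0.001 | 0.602 |
| 1%, 20% | 1 | 0.002 | 0.604 |
| 3%, 35% | 0.5 | 0.00525 | 0.611 |
| 3%, 35% | 1 | 0.0105 | 0.623 |
| 5%, 50% | 0.5 | 0.0125 | 0.627 |
| 5%, 50% | 1 | 0.025 | 0.654 |

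Mid-range shift: 1.1 points (0.611 − 0.600) to 2.3 points (0.623 − 0.600). The last row takes every input at its maximum, with one DLT in five being albumin-only (5% of 25%), and is not a likely case.

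**The case against.** The strongest reply is that this is a choice of laboratory panel. Any rule that counts all Grade 3 toxicity covers analytes that are not scheduled: Section 9.1.8 also names lipase, amylase, CPK and INR, and Section 8.1 schedules none of them. Both sections can be followed as written, so there is no contradiction. That stands. Albumin differs in that the protocol itself reports it as a DLT of this drug on a weekly schedule.

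The event may also be rare at these doses. The adult trial with this DLT had an MTD of 6 mg/m², above the top level here of 4 mg/m². In the adult trial with a recommended dose of 4 mg/m² (weekly for three weeks of four), the reported DLTs were hypophosphatemia and asthenia. The Likely (>20%) column in Section 9.1.8 is not a Grade 3 rate. All this stands and limits the size.

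Sites may draw albumin anyway, clinically apparent events are still followed under Section 10.1, and Section 14.4.2 has the study chair's evaluability and DLT calls reviewed weekly. These safeguards reduce the risk, but none requires the test.

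A reader might infer that every four-dose patient who does not start Cycle 2 goes untested. The documents do not support that: failed repeat labs, or labs already drawn in the 72-hour window, mean a value is expected. A reader might equally infer that every early stopper is replaced; Section 11.2.1 says so only for dose escalation.

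**Conclusion.** The mismatch holds in a narrow form. An attributable Grade 3 or greater albumin fall in Cycle 1 is a DLT, and no section requires an albumin value after baseline from a patient who takes all four doses and leaves before the pre-Cycle 2 labs. That patient can be scored DLT-free. PK-expansion patients who stop earlier may fall in the same gap.

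The direction is certain: the schedule can only lose such events. The size is not known and is probably small. The shift of about 1 to 2 points rests entirely on assumed rates and should not be cited as an estimate of bias. It would be too strong to say that the MTD rule is invalid or that a wrong dose is likely to be selected; nothing in the documents shows how often a Grade 3 albumin fall occurs at 3 or 4 mg/m², or how many patients leave at that point.

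A fall that recovers before the pre-Cycle 2 draw could also be missed. The documents do not show that this happens, and the conclusion does not depend on it. This is a cheap improvement to how the primary endpoint is ascertained.

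**What to change.** In the Section 8.1 table, add albumin to the chemistry already drawn weekly in Cycle 1.

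At minimum, require one end-of-Cycle-1 albumin in every treated patient, whether or not Cycle 2 starts, unless consent is withdrawn. It can be drawn with the Day 28 PK sample, which Appendix VI already asks for in patients removed from therapy after the Day 22 dose. This version fills the zero for the four-dose patient but leaves earlier weeks unobserved.

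Once albumin is in the Cycle 1 schedule, the monitoring condition in Section 11.2.1 can be read to include it.

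The cost is one added analyte and a schedule-table amendment, with no new visit or procedure. The DLT rule, doses and treatment holds stay as they are.
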